9.3. Level of Significance

No formal statistical tests will be performed. All CIs will be 95%.

9.4. Statistical Analyses

9.4.1. Primary Analyses

The primary endpoint is ORR at Day 28, defined as the proportion of subjects demonstrating a CR, VGPR, or PR, as per standard criteria (Appendix B). The primary analysis will be conducted once the last subject completes the Day 28 visit or withdraws from the study.

Summary statistics and 95% CI will be provided.

9.4.2. Secondary Analyses

The key secondary endpoint is 6-month DOR, defined as the time from first response until GVHD progression or death. Six-month DOR will be assessed when all subjects complete the the Day 180 visit. The duration of disease control will be estimated by the Kaplan-Meier method.

Additional secondary endpoints will be analyzed as follows:

- ORR, defined as the proportion of subjects demonstrating a CR, VGPR, or PR at Days 14, 56, and 100. Summary statistics and applicable 95% CI will be provided.
- Three-month DOR, defined as the time from first response until GVHD progression or death, when all subjects complete the Day 84 visit.
- NRM, defined as the proportion of subjects who died due to causes other than malignancy relapse at Months 6, 9, 12, and 24. Cumulative incidence rates will be provided. Summary statistics and applicable 95% CI will be provided.
- Relapse rate, defined as the proportion of subjects whose underlying malignancy relapses. The cumulative incidence rate and summary statistics will be provided.
- Relapse-related mortality rate, defined as the proportion of subjects whose malignancy relapses and has a fatal outcome. The cumulative incidence rate and summary statistics will be provided.
- FFS, defined as the proportion of subjects who are still alive, have not relapsed, have not required additional therapy for acute GVHD, and have not demonstrated signs or symptoms of chronic GVHD, at Month 6. The Kaplan-Meier method will be used. Summary statistics will be provided.
- Overall survival, defined as the time from study enrollment to death due to any cause. The Kaplan-Meier method will be used. Summary statistics will be provided.
- Clinical safety data (eg, AEs, infections) will be tabulated and listed.
- The plasma PK of ruxolitinib will be analyzed using a model-independent approach.

9.4.4. Safety Analyses

9.4.4.1. Adverse Events

A TEAE is either any AE reported for the first time or worsening of a pre-existing event after first dose of study drug. Analysis of AEs will be limited to TEAEs, but data listings will include all AEs, regardless of their timing to study drug administration. Adverse events will be tabulated by the MedDRA preferred term and system organ class. Severity of AEs will be based on the NCI CTCAE v4.03.

The subset of AEs considered by the investigator to have a relationship to study drug will be considered to be treatment-related AEs. If the investigator does not specify the relationship of the AE to study drug, then the AE will be considered treatment-related. The incidence of AEs and treatment-related AEs will be tabulated.

9.4.4.2. Clinical Laboratory Tests

Laboratory test values outside the normal range will be assessed for severity based on the normal ranges for the clinical reference laboratory. The incidence of abnormal laboratory values and shift tables relative to baseline will be tabulated.

Laboratory data will be classified into CTC grades for AEs (CTCAE v4.03). The following summaries will be produced for the laboratory data:

• Number and percentage of subjects with worst postbaseline CTC grade (regardless of baseline value) will be summarized. Each subject will be counted only for the worst grade observed postbaseline.

- Shift tables using CTC grades to compare baseline with the worst postbaseline value will be produced with CTC grade.
- For laboratory parameters where CTC grades are not defined, shift tables to the worst postbaseline value will be produced using the low/normal/high classifications based on laboratory reference ranges.

9.4.4.3. Vital Signs

Descriptive statistics and mean change from baseline will be determined for vital signs (blood pressure, pulse, respiratory rate, and body temperature) at each assessment time. Vital sign results will be reviewed for clinically notable abnormalities (see Table 10), and subjects exhibiting clinically notable vital sign abnormalities will be listed. A value will be considered an "alert" value if it is outside the established range and shows a > 25% change from baseline.

 Table 10:
 Criteria for Clinically Notable Vital Sign Abnormalities

Parameter	High Threshold	Low Threshold
Systolic blood pressure	>155 mmHg	< 85 mmHg
Diastolic blood pressure	> 100 mmHg	<40 mmHg
Pulse	> 100 bpm	< 45 bpm
Temperature	> 38°C	< 35.5°C
Respiratory rate	> 24/min	< 8/min

9.4.4.4. Electrocardiograms

Descriptive statistics and mean change from baseline will be determined for each ECG parameter at each assessment time. Electrocardiogram results will be reviewed for clinically notable abnormalities according to predefined criteria (Table 11). Subjects exhibiting clinically notable ECG abnormalities will be listed. Adverse events will be reported for clinically notable abnormalities that are considered clinically significant in the judgment of the investigator.

Table 11:	Criteria for Clinically Notable Electrocardiogram Abnormalities
-----------	---

Parameter	High Threshold	Low Threshold
QTcF	> 460 msec	< 295 msec
PR	> 220 msec	< 75 msec
QRS	> 120 msec	< 50 msec
QT	> 500 msec	< 300 msec
RR	> 1330 msec	< 600 msec

QTcF = Fridericia correction.

9.4.5. Pharmacokinetic Analysis

The PK parameters of C_{max} , T_{max} , C_{min} , AUC_{0-t}, and CL/F will be calculated from the blood plasma concentrations of ruxolitinib using standard noncompartmental (model-independent) PK methods. Pharmacokinetic calculations will be performed, if appropriate, using commercial software such as WinNonlin[®] (Pharsight Corporation, Mountain View, CA). Nominal times will be used in all cases, except when the difference between the actual time and nominal time is greater than 15 minutes for samples collected up to 4 hours after administration and greater than 30 minutes for samples collected more than 4 hours after administration; in these cases, actual time will be used for PK analysis.

If there is a sufficient amount of plasma concentration data from this study, then the data will be analyzed by standard population PK methods using appropriate software (eg, NONMEM).

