Hepatitis screening	7.5.6.4	Х		•													
Serum pregnancy test (childbearing females only)	7.5.6.3	х										х					
Urine pregnancy test ^e (childbearing females only)	7.5.6.3			х													
PK assessment ^f	7.7		х		Х	Х											
Correlative study blood collection	7.8	х	x		х	х		х				\mathbf{X}^{g}	х	х	х	х	

^a A ± 2-day window is permitted to facilitate scheduling during the treatment phase.
 ^b Day 1 laboratory assessments do not need to be repeated if screening assessments were performed in preceding 7 days.
 ^c After Day 56, visits will occur every 28 days and will include all Day 56 assessments.

^d The Day 365 visit will also serve as the regularly scheduled visit occurring every 28 days after Day 56 (ie, Day 364).

* Urine pregnancy tests are only required if medically indicated and should be confirmed with a serum pregnancy test.

^f Samples to be collected at predose and at 1 hour \pm 15 minutes, at 2 hours \pm 30 minutes, and between 4 and 8 hours postdose. ^g Day 56 only.

Serum Chemistries	Hematology ^a	Other
Albumin	Hematocrit	Serum pregnancy test
ALP	Hemoglobin	Urine pregnancy test ^b
ALT	Mean corpuscular volume	
AST	Platelet count	
Bicarbonate	Red blood cell count	
Blood urea nitrogen	Reticulocyte count	
Calcium	White blood cell count	
Chloride	White blood cell differential (5 parts):	Hepatitis Screening Tests
Creatinine	Basophils	
Glucose	• Eosinophils	Hepatitis B surface antigen
Lactate dehydrogenase	• Lymphocytes	Hepatitis B surface antigen antibody
Phosphorus	Monocytes	Hepatitis B core antibody
Potassium	Neutrophils	Hepatitis C virus antibody
Sodium	·······	HCV-RNA
Total bilirubin		HEV-KNA HBV-DNA
Total protein		

 Table 7:
 Clinical Laboratory Analytes

ALP = alkaline phosphatase.

^a Hematology and chemistry assessments will be performed locally.

^b Urine pregnancy tests are only required if medically indicated.

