7.7. Pharmacokinetic Assessments

7.7.1. Blood Sample Collection

Pharmacokinetic samples will be obtained on Days 1, 7, and 14. On each of these days, a predose blood sample will be drawn, study treatment will be administered, and serial blood samples will be taken at the intervals shown in Table 9.

The exact date and time of the PK blood draws will be recorded in the eCRF along with the date and time of the last dose of study drug preceding the blood draw (if applicable) and the time of the most recent meal. Instructions for sample preparation and shipping will be provided in the Laboratory Manual. Subjects will receive reminder cards in advance of the study visit providing instruction to hold the dose of study drug on the day of the visit, as well as a place to record the time of the previous dose of study drug and time of the most recent meal or snack consumed.

If PK samples are missing for a subject, PK sample collection should be performed at the next visit. On Days 1, 7, and 14, subjects must refrain from taking study medication before arriving for the visit. Subjects should not have consumed any food within 8 hours before arriving at the clinic. A trough (predose) PK sample (30-minute window) should be drawn at each of the PK visits. Following the trough PK sample, the subject should take the assigned dose of study treatment, and subsequent timed samples will be taken. Food should be withheld until 1 hour after study drug administration.

Study Day	Timing of Sample Relative to INCB018424 Administration								
Day 1	Predose	1 h ± 15 min	2 h ± 30 min	4-8 h					
Day 7	Predose	1 h ± 15 min	2 h ± 30 min	4-8 h					
Day 14	Predose	1 h ± 15 min	2 h ± 30 min	4-8 h					

 Table 9:
 Pharmacokinetic Sample Collection Time and Windows

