7.4. Pharmacokinetic Analyses

Noncompartmental analysis of the observed PK concentration data will be performed, and PK parameters, such as C_{max} , t_{max} , AUC, and $t_{\frac{1}{2}}$, will be generated and summarized wherever possible. Planned tables, listings, and figures are listed in Appendix B.

The population PK of ruxolitinib in subjects with myelofibrosis (MF) has been established in the previous MF New Drug Application. First, the PK data from this study will be applied to validate the final PK model established in the MF population. If significant biases are observed in this validation process, then a new population PK model may be generated based on the data from this study, and the model development process will follow the methods below. The data from this study may be combined with data from other clinical studies to improve parameter estimation.

The model development process consists of base pharmacokinetic model development and covariate analysis. In the base model development, compartment models with first-order absorption and linear elimination will be tested for their ability to characterize the PK of ruxolitinib in combination with corticosteroids for the treatment of steroid-refractory acute GVHD. Interindividual variability will be modeled using an exponential error model and explored for each PK parameter. Proportional, additive, and mixed error (additive plus proportional) models will be individually evaluated for their ability to describe the magnitude of residual variability. The first-order conditional estimation method with the interaction option will be used.

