Correlative study blood collection	7.8	X	Х		Х	Х		Х				X ^g	Х	Х	Х	Х	

^a $A \pm 2$ -day window is permitted to facilitate scheduling during the treatment phase.

^b Day 1 laboratory assessments do not need to be repeated if screening assessments were performed in preceding 7 days.

^c After Day 56, visits will occur every 28 days and will include all Day 56 assessments.

^d The Day 365 visit will also serve as the regularly scheduled visit occurring every 28 days after Day 56 (ie, Day 364).

^e Urine pregnancy tests are only required if medically indicated and should be confirmed with a serum pregnancy test.

^f Samples to be collected at predose and at 1 hour \pm 15 minutes, at 2 hours \pm 30 minutes, and between 4 and 8 hours postdose.

^g Day 56 only.

Tables

Table No.	Title
Table 1	Randomization of the Study
Table 2	Accuracy and Precision of the Plasma Assay Quality Control Samples
Table 3	Plasma Sample Collections Times With Deviations
Table 4	Summary of INCB018424 Pharmacokinetic Parameters From Observed Concentration Data
Table 5	Estimation of INCB018424 Population Pharmacokinetic Model Parameters
Table 6	Summary of INCB018424 Pharmacokinetic Parameters From Predicted Concentration Data
Table 7	Observed INCB018424 Plasma Concentrations for Individual Subjects
Table 8	INCB018424 Pharmacokinetic Parameters for Individual Subjects From Observed
	Concentration Data
Table 9	Predicted INCB018424 Plasma Concentrations for Individual Subjects From Final PK Model
Table 10	INCB018424 Pharmacokinetic Parameters for Individual Subjects From Predicted
	Concentration Data

Figures

Figure No.	Title
Figure 1	INCB 018424 Plasma Concentrations (Mean ± SE) Profile from Observed Concentration Data
Figure 2	Basic Goodness of fit diagnostic plots for population PK model
Figure 3	Additional Goodness of fit diagnostic plots for population PK model (optional)
Figure 4	Visual Predictive Check Plot
Figure 5	Individual Plot for Final PK

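### The PK analysis uses nominal sampling times within a tolerance although exact times are recorded, and the rule cannot be applied to the 4-8 h sample, which has no nominal time

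*Protocol*

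**What the plan says.** Protocol 9.4.5 derives Cmax, Tmax, Cmin, AUC0-t and CL/F "using standard noncompartmental (model-independent) PK methods". Its time rule is: "Nominal times will be used in all cases, except when the difference between the actual time and nominal time is greater than 15 minutes". That limit covers draws up to 4 h after dosing. Beyond 4 h the exception needs a difference "greater than 30 minutes for samples collected more than 4 hours after administration". Past either limit, "in these cases, actual time will be used for PK analysis".

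Protocol 7.7.1 and Table 9 schedule four samples on each of Days 1, 7 and 14: predose, 1 h ± 15 min, 2 h ± 30 min, and a last one given only as an interval. Footnote f to Table 6 words that last sample as "and between 4 and 8 hours postdose". The SAP copy of the schedule gives the same interval.

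The recorded times exist. Protocol 7.7.1 states: "The exact date and time of the PK blood draws will be recorded in the eCRF", together with the time of the preceding dose.

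SAP 7.4 neither repeats nor replaces the rule. It says only: "Noncompartmental analysis of the observed PK concentration data will be performed, and PK parameters, such as" Cmax, tmax, AUC and half-life will be produced where possible. The SAP's list of planned PK tables includes one titled "Plasma Sample Collections Times With Deviations", which needs a nominal time as its reference.

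**The concern.** Rounding times that have been recorded exactly adds error for no gain. With only three postdose samples, each shift in a time value passes straight into a trapezoidal AUC. AUC and CL/F are named secondary PK endpoints, and the SAP plans tables of individual-subject parameters, where random shifts do not average out.

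The rule also does not fit the schedule. The last sample fixes t in AUC0-t, and it is the only scheduled sample that can fall after 4 h. The 30-minute clause therefore governs only a sample that has no nominal time to be measured against. Two analysts following 9.4.5 could treat that sample differently, and neither would be departing from the text.

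**Working it through.** The documents give no figure for timing error, so there is none to reproduce. The first step uses the documents alone. The later steps illustrate size on assumed values.

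**1. Window against tolerance (Table 9 and 9.4.5)**

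| Sample | Permitted window | Tolerance | Time used when in window |
|---|---|---|---|
| 1 h | ± 15 min | 15 min | Always 60 min, even if drawn at 45 or 75 min |
| 2 h | ± 30 min | 15 min | Nominal up to 15 min off, actual from there to 30 min off |
| 4-8 h | any time in a 4-hour interval | 15 min if drawn at 4 h, otherwise 30 min | Undefined: no nominal time |

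A 2 h sample drawn 15 minutes late is analysed at 2.00 h. One drawn 16 minutes late is analysed at 136/60 = 2.27 h.

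**2. Worst case for one subject, 1 h and 2 h samples**

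Assumptions, none from the documents: one-compartment oral model at steady state with dosing every 12 h; half-life 2-4 h; ka 1.5-5 per hour; last sample at 6 h, analysed at its actual time.

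Formula: AUC0-t = Σ (t[i+1] − t[i]) × (C[i] + C[i+1]) / 2, computed with actual and then with nominal times on the same concentrations. Error = AUC(nominal)/AUC(actual) − 1.

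Example with half-life 2 h and ka 5, draws at 0, 0.75, 2.25 and 6 h. Concentrations in units of F × dose/V are 0.0171, 0.8164, 0.5005 and 0.1364.

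- Interval means: 0.4167, 0.6584, 0.3184.
- Actual times: 0.75 × 0.4167 + 1.5 × 0.6584 + 3.75 × 0.3184 = 2.494.
- Nominal times: 1 × 0.4167 + 1 × 0.6584 + 4 × 0.3184 = 2.349.
- Error: 2.349/2.494 − 1 = −5.8%.

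Taking each deviation as −15, 0 or +15 minutes, the extremes are −5.8% to +6.2% at half-life 2 h and −3.8% to +4.0% at half-life 4 h. A wider grid (half-life 2-6 h, ka 1-4 per hour, first dose and steady state, last sample at 4, 6 or 8 h) gives −6.5% to +7.4%.

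**3. Typical size**

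With draw times uniform over the permitted windows, the 9.4.5 rule applied to the 1 h and 2 h samples, and actual time for the last sample, the error in AUC0-t has mean about 0.0% and SD 1.4-2.1%. For 95% of subjects it is within about 2.5-4.1%.

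**4. Last sample**

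If actual time is used, the timing error is zero. If an analyst chose 6 h as nominal and applied the 30-minute tolerance, the combined error with step 2 would run from −11.6% to +15.0%. The documents assign neither 6 h nor any other value.

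**5. What actual times do not cure**

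On the step 2 model, with every time exact, trapezoidal AUC0-8 is 1.55-1.72 times AUC0-4. For otherwise identical subjects whose last draw is uniform over 4-8 h, AUC0-t has a coefficient of variation of about 12-15%, several times the 1.4-2.1% from rounding.

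**The case against.** The strongest reply is that using nominal time within a stated tolerance is a prespecified choice with little effect here. Rounding is close to unbiased, so group summaries hardly move. PK is a secondary objective, summarised descriptively with no hypothesis or threshold. The measured Cmax and Cmin values do not depend on the time label. SAP 7.4 says little about the noncompartmental analysis and describes population PK at length. All of this stands and limits the weight of the point. It does not answer the gap for the last sample, or explain why rounding is preferred when exact times are in the database.

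A reader might infer three stronger things, and the documents support none of them:

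- **Recorded times are discarded altogether.** They are not. Actual time applies beyond the tolerance, which covers half of the permitted 2 h window. Only the 1 h sample is always set to nominal when in window.
- **AUC0-t is wrong by 12-15%.** That range needs a 6 h nominal for the last sample, which neither document states. With no nominal time given, an analyst may well use the recorded one, and the last-sample error is then zero. The defect is an undefined rule, not a demonstrated error of that size.
- **Error in AUC0-t passes directly into CL/F.** The documents do not say which AUC gives CL/F, and an AUC truncated at 4-8 h would not in general give clearance, however the times are labelled.

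**Conclusion.** The point holds as a minor, cost-free improvement. From the text alone, 9.4.5 rounds times that are known exactly, treats 2 h samples by two conventions, and cannot be applied to the 4-8 h sample. SAP 7.4 does not repair this.

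The size is modest: at most about 4-6% either way in one subject's AUC0-t from the 1 h and 2 h samples, with SD about 1.4-2.1% and almost no bias in means. These figures rest on an assumed one-compartment model, half-life, absorption rate and, for the SD, uniform draw times. No size can be given for the last sample, because it depends on a convention that the documents leave open. The variable end point of AUC0-t is a larger source of spread than the rounding. The Day 28 response endpoint is not touched. The documents do not say which times the population PK analysis uses, so nothing is concluded about it.

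**What to change.** In Protocol 9.4.5, replace the nominal-time sentence with the following, and repeat it in SAP 7.4:

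> Actual elapsed times from the recorded dose and draw times will be used for all noncompartmental calculations, including the 4-8 h sample; nominal times will be used only for labelling summary tables and mean plots.

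Also name a common AUC interval for all subjects and the AUC from which CL/F is derived. For the planned table of collection-time deviations, say that the last sample is judged against its 4-8 h window.

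The cost is a few lines of text. The times are already collected, so no new data, visits or procedures are needed.

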9.5. Analyses for the Data Monitoring Committee

Not applicable.

9.6. Interim Analysis

An interim analysis will be conducted when 35 subjects complete Day 28 visit. In this interim analysis, only futility will be assessed, and the study will be terminated if the lower boundary is crossed.

A group sequential design method for 1 sample binary outcome data will be used to calculate the lower boundary of futility. The spending function of HSD(-4) will be used. For H0: p = 0.4, Ha: p = 0.6, and a 1-sided binomial test with alpha of 0.025, if ≤ 15 subjects respond at the time of the interim analysis, the study will be terminated. This will provide 70.03% probability for the response rate of 40% at the interim analysis.

If \geq 37 subjects respond at the time of final analysis, the study outcome will be considered positive. These assumptions will provide 89.88% power for the response rate of 60% in the final analysis with Type I error of 0.0189.

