3	Maculopapular rash > 50% BSA	6.1-15 mg/dL	_	Adult: > 1500 mL/day or > 7 episodes/day. Child: > 30 mL/kg per day or > 10 episodes/day.
4	Generalized erythroderma (> 50%) with bullae	> 15 mg/dL	_	Severe abdominal pain with or without ileus or grossly bloody stool (regardless of stool volume).

BSA = body surface area.

Overall clinical grade (based on most severe target organ involvement):

Grade 0: No Stage 1-4 of any organ.

Grade I: Stage 1-2 skin without liver, upper GI, or lower GI involvement. Grade II: Stage 3 rash and/or stage 1 liver and/or stage 1 upper GI and/or stage 1 lower GI. Grade III: Stage 2-3 liver and/or Stage 2-3 lower GI, with Stage 0-3 skin and/or Stage 0-1 upper GI.

Grade IV: Stage 4 skin, liver, or lower GI involvement, with Stage 0-1 upper GI.

Estimated Duration of Participation: Subject participation is expected to average 12 months, which includes the following:

- A screening period lasting up to 28 days.
- A treatment period lasting as long as the subject is deriving benefit (estimated 9 months).
- A safety follow-up period lasting 30 to 35 days after treatment ends.
- A survival follow-up period lasting until death, withdrawal of consent, or the end of the study, whichever occurs first.

Estimated Number of Subjects: 70

Estimated Number of Study Sites: 40

Principal Coordinating Investigator: TBD

Statistical Methods:

Approximately 70 subjects are planned for the final analysis of the primary endpoint. A treatment regimen for steroid-refractory GVHD demonstrating an absolute improvement of 20% versus historic data would be considered clinically meaningful. With the assumed true rate of 60%, a sample size of 70 subjects would provide > 90% probability to have a 95% confidence interval with lower limit of \geq 40%. An interim analysis will be performed for futility once 35 subjects complete the Day 28 visit; if the lower boundary is crossed, the study will be terminated.

TABLE OF CONTENTS

SYNOPSIS	5	3
LIST OF A	BBREVIATIONS	15
1.	INTRODUCTION	18
1.1.	Overview of Acute Graft-Versus-Host Disease	18
1.1.1.	First-Line Treatment of Acute GVHD	19
1.1.2.	Treatment for Steroid-Refractory Acute GVHD	20
1.2.	Ruxolitinib Background	21
1.2.1.	Pharmacology	21
1.2.2.	Clinical Studies	22
1.3.	Study Rationale	23
1.3.1.	Animal Studies in Acute GVHD Models	23
1.3.2.	Clinical Experience With JAK Inhibitors for the Treatment of Acute GVHD	24
1.3.3.	Rationale for Chosen Endpoints	25

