4.4. Duration of Treatment and Subject Participation

After signing the informed consent form (ICF), screening assessments may be completed over a period of up to 28 days. Each subject enrolled in the study may continue to receive study treatment for as long as benefit is observed and/or treatment withdrawal criteria are not met. If

the subject discontinues study treatment (ie, ruxolitinib and corticosteroids), then the treatment period will end, and the subject will enter the follow-up period (see Section 6.4). The safety follow-up period will last 30 to 35 days, and the survival follow-up period will last until death, withdrawal of consent, or the end of the study, whichever occurs first. Study participation is expected to average approximately 12 months per individual subject.

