4.5. Overall Study Duration

The study begins when the first subject signs the informed consent. Subjects who are still receiving study treatment at the time of the primary analysis will be permitted to continue on study treatment until treatment withdrawal criteria are met (Section 5.5). All subjects will be followed for survival until death, withdrawal of consent, or the end of the study, whichever occurs first. The study will end and the final analysis will occur once 75% of subjects have achieved 2-year NRM, died or are lost to follow-up, whichever occurs first.

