5.5.1. Withdrawal Criteria

Subjects **must** be withdrawn from study treatment for the following reasons:

- The subject has experienced an unacceptable toxicity.
- Relapse of the underlying malignancy.
- The subject is unable to tolerate ruxolitinib at a dose of 5 mg QD.
- Additional systemic therapy is required for GVHD progression or lack of response, including corticosteroids equal to or greater than the dose used on Study Day 1.
- Further participation would be injurious to the subject's health or well-being, in the investigator's medical judgment.
- The subject becomes pregnant.

- Consent is withdrawn.
- The study is terminated by the sponsor.
- The study is terminated by the local health authority, IRB, or IEC.

A subject **may** be withdrawn from study treatment as follows:

- If, during the course of the study, a subject is found not to have met eligibility criteria, then the medical monitor, in collaboration with the investigator, will determine whether the subject should be withdrawn from the study.
- If a subject is noncompliant with study procedures or study drug administration in the investigator's opinion, then the sponsor should be consulted for instruction on handling the subject.

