3.2. Sample Size Considerations

Approximately 70 subjects are planned for the final analysis of the primary endpoint of ORR. A second-line treatment demonstrating a true ORR of 60% would be considered clinically meaningful. With the assumed true rate of 60%, a sample size of 70 subjects would provide > 90% probability to have a 95% CI with lower limit of \ge 40%.

An interim analysis will be conducted once 35 subjects complete the Day 28 visit. In this interim analysis, only futility will be assessed, and the trial will be terminated if the lower boundary is crossed.

A group sequential design method for 1 sample binary outcome data will be used to calculate the lower boundary of futility. The spending function of HSD(-4) will be used. For H0: p = 0.4, Ha: p = 0.6, and a 1-sided binomial test with alpha of 0.025, if ≤ 15 subjects respond at the time of the interim analysis, the study will be terminated. This will provide 70.03% probability for the response rate of 40% at the interim analysis.

If \geq 37 subjects respond at the time of final analysis, the study outcome will be considered positive. These assumptions will provide 89.88% power for the response rate of 60% in the final analysis with Type I error of 0.0189.

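### A futility stop ends the study rather than enrolment, so Section 5.5.1 takes benefiting subjects off study treatment

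*Protocol*

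**What the plan says.** **Stopping rule.** Protocol Section 9.6 states that "only futility will be assessed, and the study will be terminated if the lower boundary is crossed", and then attaches the number: with 15 or fewer of 35, "subjects respond at the time of the interim analysis, the study will be terminated". The synopsis and Section 9.2 use "if the lower boundary is crossed, the study will be terminated". SAP Section 3.2 has "only futility will be assessed, and the trial will be terminated if the lower boundary is crossed", and SAP Section 9 repeats the protocol. Counting one statement in the synopsis and two in each of 9.2, 9.6, SAP 3.2 and SAP 9, termination appears nine times. None of them limits the action to enrolment.

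**Effect on subjects.** Section 5.5.1 has a mandatory list and a discretionary list. The mandatory list includes "The study is terminated by the sponsor". Section 4.6 gives the sponsor the power to terminate and otherwise sets notification and record-keeping duties.

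**Continuation of treatment.** Section 4.4 says that subjects "may continue to receive study treatment for as long as benefit is observed and/or treatment withdrawal criteria are not met". Section 4.5 says: "Subjects who are still receiving study treatment at the time of the primary analysis will be permitted to continue on study treatment", again only until a withdrawal criterion in Section 5.5 is met.

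**End of study.** Section 4.5 says: "The study will end and the final analysis will occur once 75% of subjects have achieved 2-year NRM, died or are lost to follow-up". It does not mention futility.

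**The concern.** A Day 28 response rate in 35 subjects informs whether more subjects should be enrolled. Whether a subject who is already responding should stop is an individual benefit-risk question. The plan settles both with one rule.

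The sponsor already accepts the distinction in one place: Section 4.5 lets subjects continue past the primary analysis. The futility branch has no matching clause. An investigator could not simply fill the gap, because Section 10.1 requires changes to protocol procedures, medical emergencies aside, to be approved by the sponsor and then the IRB/IEC. The protocol describes steroid-refractory acute GVHD as having no approved agent and a 6-month survival of 49% (Section 1.1.2), so a response on treatment should not be given up without a decision about that subject.

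**Working it through.** **1. The text.**
- Section 9.6 and its parallels: 15 or fewer of 35 leads to termination of the study. The sentence is passive, but Section 4.6 gives that power to the sponsor.
- Section 5.5.1: sponsor termination requires withdrawal from study treatment. Responders are not exempted.
- Section 4.4 does not rescue them. Its and/or is loose, but it refers back to the withdrawal criteria and cannot override an explicit requirement.
- Section 4.5 does not rescue them. The futility look is not the primary analysis, which Section 9.4.1 places after the last subject's Day 28 visit or withdrawal. The clause is also subject to Section 5.5, where sponsor termination is a criterion.
- The documents supplied contain no rollover or wind-down provision.

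**2. The plan's own figures.** Inputs from Section 9.6: interim n = 35, stop if X1 ≤ 15, success if the total is ≥ 37, null 0.40, alternative 0.60. Section 9.2 gives N = 70, so stage 2 has 70 − 35 = 35.
- Stop probability: P(X1 ≤ 15), X1 ~ Binomial(35, 0.40), = 0.7003 (plan: 70.03%).
- Type I error: sum over x = 16 to 35 of P(X1 = x) · P(X2 ≥ 37 − x), X2 ~ Binomial(35, 0.40), = 0.0189 (plan: 0.0189).
- Power: the same sum at 0.60 = 0.8988 (plan: 89.88%).

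All three reproduce.

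**3. How often, and how many responders.**

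| True ORR | P(stop) | Mean Day 28 responders given a stop | Product |
|---|---|---|---|
| 40% | 0.7003 | 12.54 | 8.78 |
| 50% | 0.2498 | 13.72 | 3.43 |
| 60% | 0.0300 | 14.29 | 0.43 |

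The third column is E[X1 | X1 ≤ 15]. It counts Day 28 responders among the 35, not subjects on drug at the stop. The only firm bound among the 35 is 15. Later enrollees come on top. With about 70 planned there could be 0 to 35 of them, and the documents give neither an accrual rate nor a pause in enrolment. The number still on drug is therefore 0 to 15 Day 28 responders among the 35, plus an unknown number of others.

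**4. Effect of stopping enrolment instead.** The sums in step 2 depend on the boundary and the final rule, not on what treated subjects do afterwards. If a crossed boundary still means failure, 0.0189 and 89.88% stand. If the boundary were ignored and all 70 enrolled, the rule of ≥ 37 of 70 would have type I error 0.0199 and power 0.909. The difference is small and still below 0.025, but the revised text should keep the boundary binding. After a crossing, a total of 37 would need at least 37 − 15 = 22 responders from later enrollees, and the text should exclude that route to a positive result.

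**The case against.** **The trigger is unlikely at the planned rate, and nothing statistical is wrong.** Both statements stand. At 60% a stop has probability 3.0%, and the estimate, boundary and error rates are unaffected. The point concerns what happens to subjects after the rule fires, chiefly when the true rate is near the null.

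**A reader might infer that responders would lose ruxolitinib altogether.** The documents do not show this. Section 5.5.1 ends study treatment only. Section 1.3.2 describes patients with steroid-refractory GVHD who received ruxolitinib in a retrospective analysis, and SAP Section 7.4 mentions an earlier New Drug Application in myelofibrosis. Neither establishes access for these subjects, but loss of access cannot be assumed.

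**A reader might contrast an abrupt stop with a planned taper for every responder.** That goes too far. Section 5.4.2.3 is permissive. It covers subjects in CR or VGPR at Day 180 who have been off steroids for at least 8 weeks, without Grade 2 or higher ruxolitinib-related hematologic toxicity or symptoms of active infection. Partial responders have no standard taper there. The protocol gives no taper on termination, but it does not forbid one.

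**A reader might infer that follow-up is lost.** The text is unclear rather than adverse. Section 5.5 says that stopping treatment is not study completion, and Section 6.4.2 continues disease-status visits. Against that, Section 5.5.2 describes a subject who stops drug as withdrawn from the study, and Sections 6.4.2 and 6.4.3 end follow-up at the end of the study.

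**The sponsor could amend after a crossing, or could stop enrolment and then terminate electively.** Both are true. The first leaves subjects dependent on an urgent amendment and IRB/IEC approval. The second means that the change removes the automatic withdrawal, not every route to it.

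**Conclusion.** The point holds as a gap in what the plan requires. If the boundary is crossed, the written text ends the study, and Section 5.5.1 then withdraws every subject still on study treatment, including up to 15 Day 28 responders among the 35 and any later enrollees. No clause lets a benefiting subject continue.

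The probability that this is triggered is 70.0%, 25.0% and 3.0% at true ORR 40%, 50% and 60%, taking the 35 outcomes as independent binomial and the boundary as binding. How many subjects would still be on drug cannot be computed, and the conditional means of 12.5 to 14.3 responders should not be read as that number or as upper bounds on it. The conclusion also assumes that a futility termination counts as termination by the sponsor, which is the natural reading of Sections 4.6 and 5.5.1.

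This is a worthwhile, inexpensive correction that protects subjects. It is not an error in the design's operating characteristics.

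**What to change.** - **Stopping rule.** In the synopsis, Sections 9.2 and 9.6, and SAP Sections 3.2 and 9 (nine statements in all), replace termination of the study or trial with: 'enrolment will be stopped and the primary objective will be declared not met'. This keeps the boundary binding, so 0.0189 and 89.88% stand.
- **Continuation.** Extend Section 4.5: 'Subjects on study treatment at a futility stop who are benefiting, in the investigator's judgment and in consultation with the medical monitor, may continue until another criterion in Section 5.5.1 applies, with taper under Section 5.4.2.3 where its conditions are met.' The medical monitor's part matters because Section 8.7 provides no formal Data Monitoring Committee review.
- **Follow-up.** State that subjects already enrolled keep the existing Day 28 assessment and the follow-up in Section 6.4 unless consent is withdrawn.
- **Other terminations.** Leave Section 4.6 as it is for termination on other grounds.

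**Cost.** Now, only protocol and SAP wording. If the boundary is crossed, the sponsor supplies drug to those who continue and follows at least 35 subjects, potentially to the end of study in Section 4.5 (75% of subjects at 2 years, dead or lost), at up to about 40 sites. The clinical downside is continued exposure to a regimen that missed its target, confined to subjects judged to be benefiting.
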